5.1. INCLUSION CRITERIA

To be eligible for inclusion into this study, each patient must fulfill the following inclusion criteria:

1. Patients accepted and listed for transplantation due to irreversible, progressive disabling, end-stage pulmonary disease.
2. Ages 18-65 years
3. Body weight 30 - 95 kg, inclusive (i.e. up to 95.99 kg).
4. Planned isolated (single and bi-lateral) lung transplant from a non-living donor with brain death. This includes lobar lung transplant involving excision and sizing of a cadaver donor lobe to meet the thoracic dimension of the recipient before being transplanted.
5. Normal renal function at the time of transplant as per calculated creatinine clearance ≥ 60 mL/min. Creatinine clearance will be calculated (CLcr) according to the Cockcroft-Gault formula (1976; see section 7.1).
6. Patient willing and able to comply with the protocol procedures for the duration of the study, including scheduled follow-up visits and examinations.
7. Patient given written informed consent, prior to any study-related procedure not part of normal medical care, with the understanding that consent may be withdrawn by the patient at any time without prejudice to their future medical care.

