5.2. EXCLUSION CRITERIA

To be eligible for inclusion into this study, each patient must not fulfill any of the following:

1. Recipients of an intended multiple organ transplant, including heart-lung and liver-lung transplantation.
2. Recipients of a lung from a living lobar donor.
3. Recipients of a lung from a non-heart beating donor.
4. Re-do lung transplantation.
5. Recipients requiring mechanical ventilation at the time of transplant.
6. Recipients with extra-respiratory tract site of infection (positive blood culture(s) and/or fever, associated with other signs of systemic sepsis syndrome). The criterion is not meant to exclude bacteremic cystic fibrosis patients with or without fever, unless they present with other signs of sepsis.
7. Recipients with hepatic dysfunction (bilirubin exceeding 3 mg/dL and/or transaminases $>3X$ upper limit of normal) at the time of transplant.

8. Hypersensitivity to:
 - a) ibuprofen or to more than one non steroidal anti-inflammatory drug (NSAID).
 - b) medications belonging to the class of sulfonamides, such as sulfamethazine, sulfamethoxazole, sulfasalazine, nimesulide or celecoxib.
9. Patients simultaneously participating in any other studies involving a study drug to be administered concomitantly with the Investigational Product and/or a study drug intended to prevent ischemia/reperfusion injury.
10. Planned use of anti-CD3 monoclonal antibody (Orthoclone OKT3) or alemtuzumab (Campath) induction immunosuppression.
11. Planned use of sirolimus in the first three months after transplantation.
12. Pregnant or breast-feeding women. (NB: pregnancy should be avoided in patients or partners during the first month of participation in the study; no other specific warnings are described, considering even stricter general recommendations concerning pregnancy in transplanted patients, the treatment course of the Investigational Product, its pharmacokinetic profile, and the lack of significant adverse effects on mating performance and fertility in animal studies).

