9.4.6. Safety analysis

Safety variables will be presented for the Safety population.

AEs will be presented, by treatment group, in terms of the incidence, severity and relationship to the study drug, overall and by body system and preferred term. SAEs will be presented in the same way.

Laboratory tests are performed at screening and at hospital discharge and shift tables will be used to present shifts from within/outside the normal range between screening and discharge.

Vital signs at each time point, the change in vital signs from screening to each time point, and cardiopulmonary physiologic measurements at each time point will be presented using descriptive statistics.

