### 9.6.4 Laboratory data

Samples for safety laboratory tests for hematology, clinical chemistry and coagulation are taken at Screening and hospital discharge. The following parameters will be included in the summary data presentations:

Hematology: hematocrit, hemoglobin, red blood cells, white blood cells, neutrophils, lymphocytes, monocytes, eosinophils, basophils

Clinical chemistry: sodium, potassium, chloride, bicarbonate, blood urea nitrogen (BUN), total bilirubin, alanine aminotransferase (ALT), aspartate aminotransferase (AST), serum creatinine

Coagulation: activated partial thromboplastin time (APTT), prothrombin time (PT), INR

Note: patients will either have a value for PT or INR at each time point.

Results for each parameter at screening and hospital discharge will be assessed as being below the lower limit of the normal range, within the normal range or above the upper limit of the normal range. The number and percentage of patients with out-of-range results and the number and percentage of patients with clinically significant out-of-range results will be presented for each parameter at each time point, together with the number of patients with results for that parameter and time point. Shifts in laboratory parameters during the hospital stay will also be presented for each parameter.

Creatinine clearance is calculated using Cockcroft-Gault formula at Screening and at 12, 24 and 36 hours post ICU admission for the assessment of renal and hepatic function during the study.

These data are used for assessment of patient during the study conduct phase and will be listed only.

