- 2.3.3 Analysis of PGD Score stratified by Centre (ITT Population)
- 2.3.4 Analysis of PGD Score stratified by Centre (PP Population)
- 2.4.1 Time to Freedom from Mechanical Ventilation (ITT Population)
- 2.4.2 Time to Freedom from Mechanical Ventilation (PP Population)
- 2.4.3 Time to Freedom from Mechanical Ventilation by Type of Transplant (ITT Population)
- 2.4.4 Time to Freedom from Mechanical Ventilation by Type of Transplant (PP Population)
- 2.5.1 Duration of ICU Stay (ITT Population)
- 2.5.2 Duration of ICU Stay (PP Population)
- 2.5.3 Duration of ICU Stay by Type of Transplant (ITT Population)
- 2.5.4 Duration of ICU Stay by Type of Transplant (PP Population)
- 2.6 Mortality up to 30 Days Post-Transplant (ITT Population)
- 2.7 Pulmonary Function Tests at Month 1 (ITT Population)
- 2.8 Acute Rejection Episodes by Month 1 (ITT Population)
- 3.1 Extent of Study Drug Exposure (Safety Population)
- 3.2.1.1 Summary of Treatment-Emergent Adverse Events (Safety Population)
- 3.2.1.2 Treatment-Emergent Adverse Events by Body System and Preferred Term (Safety Population)
- 3.2.1.3 Treatment-Emergent Adverse Events by Body System, Preferred Term and Relationship to Study Drug (Safety Population)
- 3.2.1.4 Treatment-Emergent Adverse Events by Body System, Preferred Term and Severity of Event (Safety Population)
- 3.2.1.5 Treatment-Emergent Adverse Events Leading to Premature Withdrawal (Safety Population)
- 3.2.2.1 Treatment-Emergent Serious Adverse Events by Body System and Preferred Term (Safety Population)

3.2.2.2	Treatment-Emergent Serious Adverse Events by Body System, Preferred Term and Relationship to Study Drug (Safety Population)
3.2.2.3	Treatment-Emergent Serious Adverse Events by Body System, Preferred Term and Severity of Event (Safety Population)
3.2.2.4	Treatment-Emergent Serious Adverse Events Leading to Premature Withdrawal (Safety Population)
3.3.1.1	Clinically Significant Results for Hematology (Safety Population)
3.3.1.2	Clinically Significant Results for Clinical Chemistry (Safety Population)
3.3.1.3	Clinically Significant Results for Coagulation (Safety Population)
3.3.2.1	Shifts in Hematology Parameters (Safety Population)
3.3.2.2	Shifts in Clinical Chemistry Parameters (Safety Population)
3.3.2.3	Shifts on Coagulation Parameters (Safety Population)
3.4	Prior and Concomitant Medications (Safety Population)
3.5.1.1	Vital signs – Systolic Blood Pressure (Safety Population)

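### Laboratory tables sort results by normal-range category plus an undefined significance count, so no planned table compares graded hepatic or renal change between arms

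*SAP*

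**What the plan says.** SAP 9.6.4 fixes the time points: "Samples for safety laboratory tests for hematology, clinical chemistry and coagulation are taken at Screening and hospital discharge". Each result is "assessed as being below the lower limit of the normal range, within the normal range or above the upper limit of the normal range". Three tabulations follow: out-of-range counts, a count under which "the number and percentage of patients with clinically significant out-of-range results will be presented for each parameter at each time point", and shifts between screening and discharge. In the SAP's table list these become Tables 3.3.1.1 to 3.3.1.3 (the chemistry one is titled "Clinically Significant Results for Clinical Chemistry (Safety Population") and shift Tables 3.3.2.1 to 3.3.2.3. Protocol 9.4.6 asks for the same kind of display: "shift tables will be used to present shifts from within/outside the normal range between screening and discharge".

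Of creatinine clearance at screening and at 12, 24 and 36 hours, SAP 9.6.4 says: "These data are used for assessment of patient during the study conduct phase and will be listed only". The outputs are Listings 4.15.4 and 4.15.5.

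The protocol uses other scales for the same organs. Protocol 5.1 requires "Normal renal function at the time of transplant as per calculated creatinine clearance" of at least 60 mL/min. Protocol 5.2 excludes "bilirubin exceeding 3 mg/dL and/or transaminases $>3X$ upper limit of normal", and Protocol 6.3.2 uses the same hepatic limits as a criterion for stopping the infusion. The renal criterion in 6.3.2 is a conjunction: CLcr below 60 mL/min together with urine output below 0.5 mL/kg/hour, on two consecutive samples among 12, 24 and 36 hours.

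**The concern.** The kidney and the liver are the two organs for which the protocol sets both entry limits and stopping criteria, and safety is a stated objective. Yet the laboratory tables use a scale that does not contain those limits. A patient can move a long way on the protocol's scale without changing category. The converse also occurs: very different changes land in one category. The only graded element is the clinically significant count. Neither document defines that term, and the count covers out-of-range results only.

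The plan's general rule points the other way. Protocol 9.4 and SAP 9.1 call for means, standard deviations, medians and ranges for continuous data, and SAP 9.6.6 gives vital signs both values and change from screening. Creatinine, bilirubin, ALT and AST get neither. At stake is whether the Month 1 report can show, by arm, a difference in graded renal or hepatic change if one exists.

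**Working it through.** The plan gives no figure to reproduce here. The check is to classify eligible patients under both scales.

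**Hepatic (multiples of ULN, so no outside figure needed for transaminases)**

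Entry is allowed up to 3 × ULN (Protocol 5.2). The threshold during infusion is above 3 × ULN (Protocol 6.3.2).

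| Screening | Later value | Fold rise | Crosses 3 × ULN | Shift category |
|---|---|---|---|---|
| 1.5 × ULN | 10 × ULN | 10/1.5 = 6.7 | yes | above to above: none |
| 2.0 × ULN | 3.1 × ULN | 3.1/2.0 = 1.55 | yes | above to above: none |
| within range | 1.1 × ULN | – | no | within to above |
| within range | 10 × ULN | – | yes | within to above |

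The first two rows are no shift, and each such patient counts as out of range at both time points. The last two rows are indistinguishable. Bilirubin behaves the same way for a screening value between ULN and 3 mg/dL, assuming the local ULN is below 3 mg/dL.

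**Renal (formula from Protocol 7.1)**

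CLcr = (140 − age) × weight / (creatinine in mmol/L × 815), multiplied by 0.85 for women. The documents give no normal ranges, so every creatinine ULN below is an assumption.

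- Woman, 60 years, 55 kg: numerator 80 × 55 × 0.85 = 3740. Creatinine 0.060 mmol/L gives 3740/48.90 = 76.5 mL/min; 0.078 gives 3740/63.57 = 58.8. Both values are within range for any assumed female ULN of 0.080 or more.
- Woman, 50 years, 55 kg, creatinine 0.6 to 1.0 mg/dL (1 mg/dL = 0.0884 mmol/L): 97.3 to 58.4 mL/min. Within range if ULN is 1.0 to 1.1 mg/dL.
- Man, 60 years, 60 kg, creatinine 0.7 to 1.2 mg/dL: 95.2 to 55.5 mL/min. Within range if ULN is 1.2 to 1.3 mg/dL.

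Each is a within-to-within result. It is not a shift, and it cannot enter the significance count.

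To see where this is possible, set CLcr = 60, solve for creatinine, and compare with the assumed ULN over an equally weighted grid of eligible ages (18–65) and weights (30–95 kg).

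| Sex | Assumed ULN, mmol/L | Share of grid cells where CLcr reaches 60 below ULN |
|---|---|---|
| Men | 0.097 / 0.106 / 0.115 | 30% / 37% / 44% |
| Women | 0.080 / 0.097 / 0.106 | 28% / 43% / 51% |

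These are shares of age-weight cells. They are not proportions of patients or events.

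**Timing**

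A value that crosses a limit at 12, 24 or 36 hours and recovers before discharge appears in no laboratory table. SAP 9.6.4 also times these samples from ICU admission, whereas Protocol 6.3.2, 7.5.2 and Appendices 4 and 6 time them from the start of infusion.

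**The case against.** The strongest defence has five parts.

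- **The SAP follows the protocol.** Protocol 9.4.6 specifies normal-range shift tables. This is correct; the point is about an uninformative choice, not a departure from the protocol.
- **Other routes exist.** The significance count could pick up the 1.5 to 10 × ULN patient. Protocol 8.1.1 lets abnormal laboratory findings be adverse events, which are tabulated by arm. Infusion duration is summarised, terminations and chemistry are listed, and 100 patients can be read line by line. Protocol 8.5 gives the data monitoring committee relevant laboratory results. So a reader who infers that the three-category scale is the sole display would be wrong. These safeguards are partial. The significance flag is undefined and blind to within-range change. Adverse events depend on reporting, and under Protocol 8.3.1, beyond 10 days after infusion or after discharge, only events judged at least possibly related are recorded. Listings make no comparison by arm.
- **CLcr below 60 is not the protocol's renal dysfunction.** This stands. A reader might infer that the worked examples meet the protocol's renal threshold. They do not: Protocol 6.3.2 also requires low urine output and two consecutive on-infusion samples, and says transient alterations do not count. CLcr below 60 is the complement of the entry criterion and one component of that definition.
- **The limits are rules about exposure during infusion, not discharge outcomes.** This also stands, and is a reason to tabulate the 12, 24 and 36 hour results as well as discharge.
- **Masking is not universal.** At the midpoint of the eligible ranges (41.5 years, 62.5 kg), CLcr reaches 60 at creatinine 1.42 mg/dL in men and 1.21 in women, above the mg/dL ULNs assumed here, so the planned table would show a shift. A hepatic crossing from a normal screening value does show as within to above.

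**Conclusion.** The point holds as a reporting gap. Apart from the undefined significance count, laboratory results are tabulated only by normal-range category at screening and discharge. No planned laboratory table compares by arm the graded hepatic change, the within-range creatinine change, or the on-treatment renal and hepatic results.

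The transaminase part rests on the documents alone. The renal part rests on assumed creatinine ULNs and applies to some eligible age-weight combinations: 30–44% of male and 28–51% of female grid cells over the ranges tried. How many patients would be affected cannot be derived, because the documents give neither the patient distribution nor the local ranges.

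Nothing here shows that repertaxin causes renal or hepatic harm, and the primary efficacy result is untouched. This is a low-cost improvement to how a stated safety objective is reported.

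**What to change.** In SAP 9.6.4 and Tables 3.3.1.2 and 3.3.2.2, keep the normal-range shifts and add, by arm:

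1. ALT and AST as at most ULN, above ULN to 3 × ULN, and above 3 × ULN; bilirubin as at most 3 versus above 3 mg/dL; each at screening, 12, 24 and 36 hours, and discharge.
2. Number and percentage with CLcr below 60 mL/min at 12, 24 and 36 hours and at discharge, and, separately, the number and percentage meeting the full Protocol 6.3.2 renal definition on treatment.
3. Median and range of values, and of the discharge-to-screening ratio, for creatinine, bilirubin, ALT and AST.

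State who judges clinical significance and on what basis. Reconcile the clock for the 12, 24 and 36 hour samples between SAP 9.6.4 and the protocol, so that the new rows carry the right time label.

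These are reporting categories taken from the protocol; they change no clinical rule and call for no new measurement. Protocol 7.1 and 7.5.2 already provide for age, sex, weight, laboratory values and urine output in the CRF, and sites supply their normal ranges under Protocol 11.3. The cost is SAP wording and a few table rows, best settled before database lock while the data are blinded. One limitation: no discharge weight is planned, so discharge CLcr would use screening weight, which should be footnoted.

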6.3.2. Criteria for discontinuation of Investigational Product

Administration of the Investigational Product should be immediately discontinued in case the patient develops renal or hepatic dysfunction defined as:

renal dysfunction: the occurrence of both CL_{cr} < 60 mL/min and urine output < 0.5 mL/kg/hour on two consecutive sampling time points (12, 24, 36 hours after the beginning of Investigational Product infusion).

hepatic dysfunction: bilirubin exceeding 3 mg/dL and/or transaminases >3X upper limit of normal).

Phase 1 studies in patients with ESRD have shown that renal function has a profound effect on plasma concentrations of a major, marginally active metabolite, carboxy-repertaxin (DF2243Y), which was found to accumulate over time along with the increased elimination half-life. Even if toxicological results to date suggest that DF2243Y does not raise any safety concern, limited experience in humans recommends to discontinue the drug in case of renal impairment as it would not be possible to predict the risk associated with elevated plasma levels. However, transient alterations of serum creatinine or urine output, as defined above, do not indicate a renal dysfunction that would cause impaired excretion of DF2243Y. Because repertaxin undergoes extensive hepatic metabolism, it is also recommended that the infusion is discontinued in case of hepatic dysfunction to avoid an increase of plasma level of repertaxin, exceeding the target and safe concentration.

CL_{cr}, urine output, bilirubin and transaminases will be evaluated at 12, 24 and 36 hours after the beginning of Investigational Product infusion. Samples will be processed immediately and results made available as soon as possible to the Investigator. Urine output will be calculated for each of the 12 hour periods: from start of infusion to 12 hours, 12-24 hours, and 24-36 hours.

Investigational Product will also be immediately discontinued in the event of any other possibly drug related occurrences that the Investigator believes might compromise patient safety.

If the Investigational Product therapy is prematurely discontinued the primary reason for discontinuation must be recorded in the CRF. Patients who discontinue the treatment with the Investigational Product will not be withdrawn from the study by default, but will complete observations as per the protocol, unless otherwise withdrawn at the Investigator's decision.

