- A BAL will be performed during mechanical ventilation, in the interval between 12 and 24 hours after reperfusion, unless the patient is suffering from any clinical conditions which would be worsened by BAL procedures, in the opinion of the Investigator (see Appendix 1 for methodological details). Date and time of sampling will be recorded in the CRF along with location of BAL (lung, site) number of aliquots injected, amount recovered and summary of the most recent chest X-rays report. Specific reasons (hemodynamic instability, severe hypoxemia, etc.) for the decision to omit the BAL should be recorded in the CRF.

Renal (CLcr, urine output) and hepatic (bilirubin, transaminases) function will be tested at 12, 24, and 36 hours after the beginning of Investigation Product infusion.

Other clinical findings, including bronchoscopic and/or BAL findings, reports for all routine chest X-rays and thoracic CT scans, and results of routine biopsy will be copied into the CRF from the medical charts. AEs will be also recorded.

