8.5. DATA MONITORING COMMITTEE

An independent Data Monitoring Committee (DMC) will be established to ensure patient safety, to consider patient risks against the potential for meeting trial objectives, and to provide recommendations to Dompé with respect to the conduct and analysis of the trial. The DMC will operate independently of Dompé, and its members will not have connections to the Sponsor with the exception of the compensation to DMC members related to DMC activities.

The DMC will comprise three voting members. They will be a multidisciplinary group that will include:

- A surgeon with extensive experience in lung transplantation,
- A physician with relevant experience in pulmonary and critical care medicine (e.g. a Medical Director of a Lung Transplant Program),
- A biostatistician.

The DMC will perform the following major functions:

- The DMC will be responsible for the ongoing review of safety data throughout the trial. Primary among the safety data that will be reviewed are serious AEs, ADRs and relevant available clinical laboratory results.
- The DMC may review acute and additional safety data, on a patient-by-patient basis, at their discretion. This review would be warranted if significant unexpected ADRs are observed.
- The DMC may request additional safety data if, in the view of the Committee, these additional data are needed in order to make an informed, responsible decision about the conduct of the study.
- The DMC will advise Dompé regarding safety of patients and continuing validity and scientific merit of the trial. The DMC will also monitor the number of deaths for both arms of the study to ensure that mortality is consistent with historical data.

All details of the conduct and responsibilities of the study DMC will be described in the 'DMC Charter' which will be finalized prior to the start of patient enrolment.

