14.4. APPENDIX 4 - STUDY FLOW CHART

Test/Examination	Screening	Tx	ICU admission	Time after ICU admission							ICU discharge	Hospital discharge	1 month	6 months	12 months
				12 h	24 h	36 h	48 h	54 h	60 h	72 h					
Informed consent	X														
Inclusion/exclusion criteria ¹	X														
Laboratory tests	X										X				
Renal/hepatic function ²	X			X ²	X ²	X ³									
Study drug administration ³		X					X ²								
Pharmacokinetic sampling ²					X ²		X ²	X ²							
PaO ₂ /FiO ₂ ratio			X		X		X			X					
Chest X-ray			X		X		X			X					
Vital signs (BP & HR) ⁴	X		X	X	X	X	X		X	X	X				
Cardiopulmonary measurements ⁴			X	X	X	X	X		X	X	X				
BAL ⁵				X ⁵											
Vital status										X	X	X	X	X	
FEV ₁ & FVC												X	X	X	
BOS score													X	X	
Cumulative acute rejection													X	X	
Adverse Events ⁶		X										X ⁶	X	X	X ⁶
Prior and concomitant medications ⁷	X											X ⁷	X	X	X ⁷

1 = Confirmatory screening to take place upon admission to the center prior to randomization

2 = (shadowed boxes) Time is from the start of study drug infusion. The '24 hours' sample is taken @ 24±6 hours; the '54 hours' sample is taken in the interval 2-6 hours after the infusion end

3 = Study drug infusion will start approximately 2 hours before the anticipated time of reperfusion

4 = Vital signs and cardiopulmonary measurements (when a PA catheter is present) will be measured up to ICU discharge or up to 5 days after ICU admission, whichever occurs earlier

5 = BAL will be performed during mechanical ventilation, in the interval between 12 and 24 hours after reperfusion

6 = All AEs will be reported up to 10 days or hospital discharge. Thereafter, only untoward events that the Investigator assesses as at least possibly related to the study drug will be recorded

7 = After 10 days or hospital discharge, only drugs used for immunosuppression, infection prophylaxis, and AEs possibly related to the study drug (see 6 above) will be recorded

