Patients will return to the center at least 30 days after the transplant for the Month 1 assessment and at 24-28 weeks and 50-54 weeks post transplant for the Month 6 and Month 12 assessments respectively. Once data up to and including the Month 1 assessment has been collected, entered and cleaned, the Month 1 database will be locked, the study will be unblinded and the primary analysis of safety and efficacy data will be performed. Data collected during the open phase of the study i.e. at Months 6 and 12 will be presented in an addendum to the main CSR.

An independent Data Monitoring Committee (DMC) has been established to ensure patient safety, to consider patient risks against the potential for meeting trial objectives, and to provide recommendations to Dompé with respect to the conduct and analysis of the trial. PPD will be responsible for providing the DMC statistician with listings of data relating to disposition (randomization, completion and withdrawal), demography, adverse events (AEs) and occurrence of clinically diagnosed PGD. Full details of the responsibilities of the DMC are provided in the DMC Charter.

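### The renal and hepatic tests taken during the infusion get no by-arm summary, are timed from ICU admission in the SAP, and are not named in its DMC listings

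*SAP*

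**What the plan says.** **Timing in the protocol.** Protocol 6.3.2 requires CLcr, urine output, bilirubin and transaminases to be "evaluated at 12, 24 and 36 hours after the beginning of Investigational Product infusion". They inform its renal and hepatic criteria for discontinuing the infusion. Protocol 7.5.2 uses the same clock: renal and hepatic "function will be tested at 12, 24, and 36 hours after the beginning of Investigation Product infusion". In the flow chart (Appendix 4) these tests sit under columns headed by time after ICU admission, but footnote 2 overrides the heading: "Time is from the start of study drug infusion". Appendix 6 allows ±4 h at each time, again from infusion start.

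**Other safety laboratory tests.** Hematology, chemistry and coagulation are sampled at screening and hospital discharge only (Protocol 4.2.4, SAP 9.6.4).

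**Timing and analysis in the SAP.** SAP 9.6.4 has creatinine clearance calculated "at Screening and at 12, 24 and 36 hours post ICU admission", and adds: "These data are used for assessment of patient during the study conduct phase and will be listed only". The matching outputs in SAP section 11 are Listings 4.15.4 and 4.15.5. SAP 1.2 declares no changes from the protocol.

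**DMC.** Protocol 8.5 names "serious AEs, ADRs and relevant available clinical laboratory results" as the primary safety data for the committee. SAP 3.1 says the DMC statistician will receive listings on disposition, demography, "adverse events (AEs) and occurrence of clinically diagnosed PGD". Both documents leave the details to the DMC Charter.

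**The concern.** Protocol 6.3.2 gives two reasons for watching these organs during the infusion. The metabolite DF2243Y accumulates when renal function is poor, and repertaxin depends on hepatic metabolism. The tests at 12, 24 and 36 h are the safety samples that bear on both while the drug is running. The tabulated laboratory results come from before the infusion and from discharge, and neither describes what happened during exposure.

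A report built to this plan would leave a reader to compare renal and hepatic function on drug by going through patient listings. A modest imbalance between arms, or a difference in how many patients met the dysfunction definitions, could go unnoticed. The wrong clock adds a second risk: a programmer who builds a summary from the SAP text alone could assign samples to the wrong time point. The shorter DMC list raises the question of whether the committee routinely receives the results that the protocol says it reviews.

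**Working it through.** The plan states no figure on this point, so the check compares the texts and adds some simple arithmetic.

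**1. Does any table carry the on-infusion values?** SAP section 11 has six laboratory tables (3.3.1.1 to 3.3.1.3 and 3.3.2.1 to 3.3.2.3). SAP 9.6.4 builds them from screening and discharge samples. The listed-only sentence refers grammatically to creatinine clearance, but the table list has no on-infusion summary of bilirubin, transaminases or urine output either. Protocol 9.4.6 plans only screening-to-discharge shifts. With 100 patients, three times and five measures (CLcr, urine output, bilirubin, ALT, AST), up to 100 × 3 × 5 = 1,500 planned values appear in listings alone. By contrast, SAP 9.6.6 summarizes blood pressure and heart rate by arm at every time point, with change from screening.

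**2. Do other tables fill the gap?** Only in part.
- The adverse event tables (SAP 9.6.2) capture a laboratory abnormality only if the investigator reports it as an event.
- The exposure table (SAP 9.6.1) gives duration and amount infused, without the reason for stopping. Infusion termination is a listing (2.5.2).
- The withdrawal tables can miss these patients, because Protocol 6.3.2 keeps those who stop the infusion in the study by default.

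**3. What would the SAP clock do to a summary?** Let d be the hours from infusion start to ICU admission. A nominal SAP time t falls at t + d on the protocol's clock. The documents do not give d, so a range is assumed.

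| Assumed d (h) | SAP 12 / 24 / 36 h, counted from infusion start | Within ±4 h? |
|---|---|---|
| 2 | 14 / 26 / 38 | yes |
| 4 | 16 / 28 / 40 | yes, at the limit |
| 6 | 18 / 30 / 42 | no |
| 8 | 20 / 32 / 44 | no |
| 12 | 24 / 36 / 48 | no; shifted by one whole time point |

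The shift equals d at every time, so any d above 4 h takes all three outside the window. The infusion starts approximately 2 h before reperfusion of the first lung (Protocol 3.1). At exactly 2 h, d passes 4 h once ICU admission comes more than 4 − 2 = 2 h after that reperfusion. Appendix 6 accepts a start as late as just over 1 h before, in which case the figure is about 4 − 1 = 3 h.

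The clock also bears on the renal definition in Protocol 6.3.2, which needs both abnormalities at two consecutive sampling times. Counting patients who met it requires each sample to be assigned to the right time.

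**4. What could a by-arm table show?** With 50 per arm and no patient meeting a definition, the one-sided 95% upper bound on the rate is 1 − 0.05^(1/50) = 5.8%. Under assumed rates of 10% and 25%, a two-sided 5% comparison would have about 51% power; with 10% and 30%, about 71%. The tables would therefore be descriptive.

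**The case against.** The case on the other side is that these samples serve patient management. Protocol 2.4.3.4 gives their purpose as checking that organ function is compatible with continuing treatment, and Protocol 4.2.4 names only the screening and discharge tests as laboratory endpoints. On the missing summary the SAP therefore follows the protocol. That stands: it is a gap in both documents, not a SAP departure.

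Several stronger readings are tempting, and the documents do not support them.
- *That samples are taken or recorded at the wrong time.* Sites follow the protocol, which uses infusion start throughout, and the SAP is to be read with it. While the data are only listed, no estimate uses the SAP clock. The error is one of wording, possibly carried over from the flow-chart column heading.
- *That the trial cannot show these results by arm.* Protocol 9.4 has CRF data listed with treatment group, so a by-arm review is laborious but possible.
- *That the DMC cannot see laboratory results.* SAP 3.1 is an overview and does not call its list exhaustive. The Charter was not available, and Protocol 8.5 lets the committee request additional safety data.
- *That this is the trial's main prespecified safety concern.* No passage says so. Protocol 6.3.2 reports that toxicology so far raises no concern about DF2243Y, and explains the rule by limited human experience.
- *That these are the only laboratory samples on drug.* Plasma drug and metabolite levels are also taken during the infusion. The claim holds for safety laboratory tests.

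**Conclusion.** The point holds in three parts of unequal weight.

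The main part is the missing summary. No planned table compares on-infusion renal or hepatic function by arm or counts patients meeting the protocol's own dysfunction definitions, and the adverse event and exposure tables are only partial substitutes. This rests on the text and the table list, with no assumption.

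The second is a plain contradiction on the clock, undeclared in SAP 1.2. Its size depends on the interval from infusion start to ICU admission, which the documents do not give. Above 4 h, all three nominal times would leave the protocol's window if the SAP clock were used to label a summary. It does no numerical harm while the data are only listed, but it must be corrected before any table is built.

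The third is that the SAP's DMC list is shorter than Protocol 8.5. The two need reconciling; what the committee actually receives cannot be judged without the Charter.

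Nothing here affects the sample size or the primary analysis. The change should be made because it concerns the only safety laboratory data taken during exposure and costs little.

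**What to change.** In SAP 9.6.4:
- Change the clock for these tests to infusion start, with the Appendix 6 window of ±4 h.
- Replace the listed-only rule with summaries by arm, in the safety population, of CLcr, bilirubin, ALT and AST at 12, 24 and 36 h, with change from screening.
- Summarize urine output by arm for each 12 h period (0–12, 12–24, 24–36 h), without change from screening, because no screening value is planned.
- Tabulate by arm the number and percentage of patients meeting each renal and hepatic dysfunction definition exactly as it stands in Protocol 6.3.2.
- Keep all of this descriptive, and add the tables to SAP section 11.

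In SAP 3.1, reconcile the DMC listings with Protocol 8.5 and the Charter: either add the laboratory results or state where they are supplied.

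The cost is two or three descriptive tables and a few lines of SAP text. The values are already collected for Listings 4.15.4 and 4.15.5. SAP 1.1 has the plan finalized before database lock, so the change can be made while the study is still blinded. No procedure, dose or sample size changes.
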